6.2 Secondary objectives

6.2.1 Variables

The secondary variables are the:

1. SCD region filling (absolute volume and % refilling) at Weeks 4, 12 and 28
2. ICRS scoring at Week 4

For SCD region filling the baseline is defined as the Day 3 assessment; for biopsy type “curette scraping” the baseline for ICRS scoring is defined as the Day 1 assessment.

6.2.2 Descriptive analyses

The variables will be listed by treatment group, patient and visit/time. Summary statistics will be provided by treatment group (LNA043 20 mg, vs.placebo) and visit/time. Summary statistics will include mean (arithmetic), SD, CV, median, minimum, maximum.

Graphical methods will be employed to show group and individual summary plots over time by treatment. Other secondary efficacy variables will be summarized graphically and in summary tables.

6.2.3 Statistical model, assumptions and hypotheses

SCD region filling

The change from baseline in SCD volume (mm³) of cartilage defect will be analyzed using similar MMRM analysis of variance **Corporate Confidential Information** A single

MMRM model will be used, since there are no layers for this secondary endpoint.

% Refilling for SCD region is derived from the following formula:

$$\% \text{Refilling}_{\text{SCD region}} = [(\text{SCD volume}_{\text{baseline}} - \text{SCD volume}_{\text{week4}}) / \text{SCD volume}_{\text{baseline}}] * 100$$

ICRS scoring at Week 4

ICRS scoring will be analyzed using an ANOVA model, by biopsy type, for treatment comparison, with scoring at Week 4 the dependent variable and treatment as fixed effect. In addition, the ICRS scoring for “curette scraping” biopsy type will be analyzed using an ANCOVA change from baseline model with treatment as fixed effect and baseline as covariate.

For both statistical analyses, model estimated means and their differences of each LNA043 dose vs. placebo, will be obtained along with the 95% CI for the difference.

Corporate Confidential Information

Corporate Confidential Information

7 Statistical methods for safety and tolerability data

All subjects within the safety analysis set will be included in the safety data analysis.

7.1 Variables

Adverse events, vital signs (blood pressure, heart rate, body temperature), ECG intervals, clinical laboratory measurements, immunogenicity, hematology, blood chemistry as well as subject demographics, baseline characteristics, and treatment information.

7.2 Descriptive analyses

Subject demographics and other baseline characteristics

All data for background and demographic variables will be listed by treatment group and subject. Summary statistics will be provided by treatment group (LNA043 20 mg vs. placebo).

Relevant medical history, current medical conditions, results of laboratory screens, drug tests and any other relevant information will be listed by treatment group and subject.

Treatment

Data for study drug administration (rescue medication) and concomitant therapies will be listed by treatment group and subject.

Vital signs

All vital signs data will be listed by treatment group, subject, and visit/time and if ranges are available abnormalities (and relevant orthostatic changes) will be flagged. Summary statistics will be provided by treatment (LNA043 20 mg vs. placebo) and visit/time.

ECG evaluations

All ECG data will be listed by treatment group, subject and visit/time, abnormalities will be flagged. Summary statistics will be provided by treatment (LNA043 20 mg vs. placebo) and visit/time.

Clinical laboratory evaluations

All laboratory data will be listed by treatment group, subject, and visit/time and if normal ranges are available abnormalities will be flagged. A separate listing is provided presenting all parameters in a subject with any abnormal values. Summary statistics will be provided by treatment (LNA043 20 mg vs. placebo) and visit/time.

Adverse events

All information obtained on adverse events will be displayed by treatment group (LNA043 20 mg vs. placebo) and subject.

The number and percentage of subjects with adverse events will be tabulated by body system and preferred term with a breakdown by treatment. A subject with multiple adverse events within a body system is only counted once towards the total of this body system and treatment.

Immunogenicity

All immunogenicity results will be listed by subject and visit/time.

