### **Corporate Confidential Information**

Development of anti-LNA043 antibodies will be monitored, as well as any potential reactions related to such antibodies, such as antibody-mediated arthropathy or impact on triglyceride metabolism, will be monitored closely with the corresponding safety plan in place.

There may be unknown risks of LNA043 which may be serious.

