#### **8.6.4.2 Clinical chemistry**

Sodium, potassium, creatinine, urea, uric acid, chloride, albumin, calcium, alkaline phosphatase, total bilirubin, LDH, GGT, AST, ALT, aPTT, PT/INR, CK, glucose, total cholesterol, LDL, HDL, triglycerides.

If the total bilirubin concentration is increased above 1.5 times the upper limit of normal, direct and indirect reacting bilirubin should be differentiated.

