**Figure 9-1 Safety monitoring**

## 9.1 Adverse events and Adverse device effects

### 9.1.1 Adverse events

An adverse event (AE) is any untoward medical occurrence (i.e., any unfavorable and unintended sign [including abnormal laboratory findings], symptom or disease) in a subject or clinical investigation subject after providing written informed consent for participation in the study until the end of study visit. Therefore, an AE may or may not be temporally or causally associated with the use of a medicinal (investigational) product.

In addition, all reports of intentional misuse and abuse of the study treatment are also considered an adverse event irrespective if a clinical event has occurred. See [Section 9.6](#) for an overview of the reporting requirements.

The occurrence of adverse events must be sought by non-directive questioning of the subject at each visit during the study. Adverse events also may be detected when they are volunteered by the subject during or between visits or through physical examination finding, laboratory test finding, or other assessments.

Abnormal laboratory values or test results constitute adverse events only if they fulfill at least one of the following criteria:

- they induce clinical signs or symptoms,
- they are considered clinically significant,
- they require therapy.

Clinically significant abnormal laboratory values or test results should be identified through a review of values outside of normal ranges/clinically notable ranges, significant changes from baseline or the previous visit, or values which are considered to be non-typical in patients with underlying disease. Investigators have the responsibility for managing the safety of individual subject and identifying adverse events. Alert ranges for liver and kidney related events are included in [Appendix 1](#) and [Appendix 2](#), respectively.

Adverse events must be recorded on the Adverse Events CRF under the signs, symptoms or diagnosis associated with them, and accompanied by the following information:

1. the Common Toxicity Criteria (CTC) AE grade (version 4.03)

If CTC-AE grading does not exist for an adverse event, use:

- 1 = mild,
- 2 = moderate,
- 3 = severe
- 4 = life threatening\* (see [Section 9.3.1](#) for definition of a serious adverse event (SAE))

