## **9.5 Renal safety monitoring**

Renal events are defined as one of the following:

- confirmed (after  $\geq 24$ h) increase in serum creatinine of  $\geq 25\%$  compared to baseline during normal hydration status
- new onset ( $\geq 1+$ ) proteinuria, hematuria or glucosuria; or as a
- doubling in the urinary albumin-creatinine ratio (ACR) or urinary protein-creatinine ratio (PCR) (if applicable).

The following two categories of abnormalities/adverse events have to be considered during the course of the study:

- Serum creatinine triggers that will require follow up and repeat assessments of the abnormal laboratory parameter
- Urine dipstick triggers that will require follow up and repeat assessments of the abnormal laboratory parameter

Every renal laboratory trigger or renal event must be followed up by the investigator or designated personnel at the trial site. Recommended follow-up assessments are listed in [Section 16-Appendix 2](#).

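### Laboratory flags are tied only to the normal range, so in-range creatinine rises that meet the protocol's own renal percentages are neither flagged nor counted by arm

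*SAP*

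**What the plan says.** SAP 7.2 plans three laboratory outputs.

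- A listing: "All laboratory data will be listed by treatment group, subject, and visit/time and if normal ranges are available abnormalities will be flagged".
- A further listing: "A separate listing is provided presenting all parameters in a subject with any abnormal values".
- A summary: "Summary statistics will be provided by treatment (LNA043 20 mg vs. placebo) and visit/time".

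Protocol 11.4.4.3 gives the first and third in equivalent terms. No redaction is visible in SAP 7.2 or in that protocol section.

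The protocol describes renal harm in different units. Section 9.5 defines a renal event as a confirmed (after at least 24 hours) "increase in serum creatinine of" 25% or more, "compared to baseline during normal hydration status", alongside urine criteria. Table 16-1 splits the creatinine criterion into rises of 25–49% and of 50% or more. Section 9.1.1 tells investigators to look for "significant changes from baseline or the previous visit" when judging whether a laboratory finding is clinically significant. Table 16-2 has renal events recorded in the CRF.

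The chemistry panel in protocol 8.6.4.2 includes creatinine and "total cholesterol, LDL, HDL, triglycerides". Protocol 3.7 mentions possible reactions to anti-LNA043 antibodies, "such as antibody-mediated arthropathy or impact on triglyceride metabolism, will be monitored closely".

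Safety is one of the two primary objectives, and blood chemistry is among its endpoints.

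**The concern.** The protocol measures renal harm as a relative change within the patient. The SAP measures laboratory findings as a position against a population range. The two can disagree. A patient who starts low in the range can meet the protocol's creatinine percentage and still sit inside the range. That patient triggers no flag, does not enter the listing of subjects with abnormal values, and adds only one more in-range number to the visit summary. No planned table says how many patients per arm met the criterion.

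The SAP sets a baseline for the MRI variables (6.1.1) and for region filling and curette histology (6.2.1), and asks for raw values and change from baseline on MRI (6.1.2). It sets neither for laboratory data. At stake is whether the summary of a primary safety endpoint can show an event that the protocol itself has defined.

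**Working it through.** The plan states no figure on this point, so there is none to reproduce. The check compares the flag rule with the renal criterion and then sizes the mismatch.

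**Step 1: when a rise escapes the flag.** A relative rise *g* from baseline *b* stays unflagged when *b*(1 + *g*) ≤ ULN, that is *b* ≤ ULN/(1 + *g*).

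- *g* = 25%: *b* ≤ ULN/1.25 = 0.80 × ULN.
- *g* = 50%: *b* ≤ ULN/1.50 = 0.67 × ULN.

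This needs no assumption about the reference range. As an illustration with an assumed range of 0.7–1.2 mg/dL, 0.80 × 1.2 = 0.96. A patient going from 0.90 to 0.90 × 1.25 = 1.125 meets the percentage and carries no flag.

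**Step 2: what share of patients start low enough.** The documents give no creatinine range. Assume ULN/LLN = *r* and baselines spread evenly within the range. The share is then (*r*/(1 + *g*) − 1)/(*r* − 1).

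| *r* (assumed) | 25% rise | 50% rise |
|---|---|---|
| 1.5 | (1.200 − 1)/0.5 = 40% | (1.000 − 1)/0.5 = 0% |
| 1.7 | (1.360 − 1)/0.7 = 51% | (1.133 − 1)/0.7 = 19% |
| 2.0 | (1.600 − 1)/1.0 = 60% | (1.333 − 1)/1.0 = 33% |

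Each entry is conditional on a rise of exactly that size. It is not a frequency of renal events. Larger rises are flagged more often.

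**Step 3: would the arm summary show it?** Twelve planned Cohort 1 completers at 2:1 give 8 on 20 mg and 4 on placebo. If one of the 8, with a baseline near the arm mean, rises by 25%, the mean moves by 0.25/8 = 3.1%; for 50% it moves by 0.50/8 = 6.3%. A by-visit mean does not identify that patient. A by-visit maximum, if given, shows the highest value and not the largest change. Actual arm sizes are not stated: the study ended early, and the safety set is everyone dosed.

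**Step 4: lipids.** The protocol gives no threshold or baseline-relative criterion for triglycerides. Out-of-range values are flagged. A shift of *x*% in every treated patient moves the arm mean by *x*% and would appear in the by-visit summary. Only an isolated change within the range is missed.

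**Step 5: liver.** The enzyme thresholds in Table 15-1 begin at 2 × ULN (ALP) or 3 × ULN (ALT, AST). All lie above the range and are flagged, so this gap does not extend to them.

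**Step 6: other routes for a renal event.** Protocol 8.6.4 requires clinically relevant laboratory deviations to be reported to the sponsor and discussed. Section 9.5 requires follow-up of every renal trigger, and Table 16-2 requires CRF recording. Section 9.1.1 lets the finding become an adverse event, which SAP 7.2 tabulates by arm. The adverse event route depends on judgement of clinical significance, and the SAP plans no output for the CRF renal records.

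**The case against.** The strongest reply has four parts.

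- **Nothing is lost.** Every value is listed by subject and visit, and in a small non-confirmatory study a reader can follow each patient's creatinine by eye. This stands, and it keeps the severity low. But the plan asks nobody to do it, and a listing gives no count by arm.
- **Raw-only is an inference.** SAP 7.2 says only that summary statistics will be given, and SAP 1.1 points to a wider set of reporting documents that we do not have. This is fair. The reading rests on the contrast with SAP 6.1.2, which names change from baseline explicitly, and on the absence of any laboratory baseline.
- **Renal events are handled case by case.** They are, for patient care and sponsor notification. What is missing is the reporting step.
- **The criterion cannot be fully derived.** Section 9.5 needs normal hydration and a repeat after at least 24 hours, and no scheduled variable for either is visible. This also stands. A programmed flag can show that the percentage was met and whether a repeat exists; it cannot adjudicate the full definition.

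A reader might also infer that a triglyceride effect would go unseen. The documents do not support that. The protocol raises it as a possible antibody-related reaction, refers to a safety plan that we do not have, and reports no anti-drug antibodies in the first-in-human study. Step 4 shows that little would be missed.

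**Conclusion.** The point holds for creatinine. Followed as written, the laboratory outputs neither flag nor count by arm a rise that meets the protocol's own percentages but stays in range. For a 25% rise this means any baseline at or below 0.80 × ULN, a result that follows from the definitions alone. The 40–60% (25% rise) and 0–33% (50% rise) shares depend on the assumed range ratio and evenly spread baselines. They show that the gap for the lower band is not a corner case and that the upper band is mostly flagged.

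It would go too far to say that such an event would be absent from the study report. The values are in the listings, and the event may reach the adverse event tables. For lipids the gap is limited to isolated within-range changes. This is a modest, inexpensive improvement to a primary-objective safety summary; it gives no reason to doubt the recorded data.

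**What to change.** In SAP 7.2, under clinical laboratory evaluations:

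1. Define the laboratory baseline as the last pre-dose value.
2. Summarise change from baseline alongside raw values by arm and visit. This display also covers the lipids, including triglycerides.
3. In addition to the normal-range flags, flag in the listing each subject whose creatinine rises 25–49% or 50% or more from baseline. Count these subjects by arm and mark whether a repeat confirmed the rise.
4. List the renal events recorded in the CRF.

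The percentages are the protocol's own, and no new clinical rule is introduced. The cost is a few derived variables, one summary table and one listing, with no new assessments. The laboratory rows of the assessment schedule are not visible in the public text, so the availability of a pre-dose chemistry value should be confirmed when the baseline is defined. Results in arms this small are descriptive only. The current SAP is dated after database lock (18-Feb-2020), so the additions must be labelled as post-lock.

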## **8.4 Subject demographics/other baseline characteristics**

Subject demographic and baseline characteristic data will be collected on all subjects. Relevant medical history/current medical conditions data will also be collected until signature of informed consent. Details are outlined in the Site Operations Manual.

Investigators have the discretion to record abnormal test findings on the medical history CRF, if in their judgment, the test abnormality occurred prior to the informed consent signature.

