#### **11.4.4.4 Adverse events**

All information obtained on adverse events will be displayed by treatment group and subject.

The number and percentage of subjects with adverse events will be tabulated by body system and preferred term with a breakdown by treatment. A subject with multiple adverse events within a body system is only counted once towards the total of this body system.

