1.4 Study design and treatment

This is a non-confirmatory, patient and investigator blinded, randomized, placebo-controlled, parallel group, 2 cohorts, single dose study in patients with cartilage lesions undergoing autologous cartilage implantation (ACI) with the use of an exploratory 7T MRI for efficacy assessment. Approximately 22 patients will be enrolled in the study to allow 18 completers, divided as follows: 12 completers in Cohort 1 and 6 completers in Cohort 2.

Participants will be treated only on one occasion (Day 1) with a single i.a. injection that will be performed under arthroscopic visualization. The two cohorts differ only by the dose administered.

Patients will be assigned to one of the following Cohorts. Each cohort has “two (2)” treatment arms in a ratio of “2:1, (LNA043: placebo)”.

Cohort 1, study treatments are defined as:

- A: single dose of 20 mg LNA043
- B: single dose of matching placebo to 20 mg LNA043

[figure not shown]
Cohort 2, study treatments are defined as:

- C: single dose of 40 mg LNA043
- D: single dose of matching placebo to 40 mg LNA043

However, due to the early termination of the study, LNA043 40mg will not be dosed.

Figure 1-1 depicts the steps that will be followed in the study for both cohorts, starting from a screening epoch, a Day 1 treatment epoch in which an arthroscopy for cartilage harvest will be done as part of the normal ACI procedure, and the patient will be dosed. Post-treatment follow-up epoch will be at Day 2, Day 3, Week 1, Week 4 (i.e., time of ACI graft implantation), Week 12 and Week 28 for the End of Study (EoS) assessments.

Figure 1-1: Study Design for Cohort 1 and Cohort 2

Corporate Confidential Information

Corporate Confidential Information

Corporate Confidential Information

4 Statistical methods: Analysis sets

For all analysis sets, patients will be analyzed according to the study treatment(s) received.

The safety analysis set will include all patients who received any study drug.

The PK analysis set will include all subjects with at least one available valid (i.e. not flagged for exclusion) PK concentration measurement, who received any study drug and with no protocol deviations that impact on PK data.

The PD analysis set will include all subjects with any available PD data, who received any study drug and experienced no protocol deviations with relevant impact on PD data.

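### Does the adverse-event summary table need an onset rule and a split at the second surgery?

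*SAP*

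**What the plan says.** SAP 7.2 plans two AE outputs. The first is a display: "All information obtained on adverse events will be displayed by treatment group (LNA043 20 mg vs. placebo) and subject". The second is a table: "The number and percentage of subjects with adverse events will be tabulated by body system and preferred term with a breakdown by treatment". The counting rule is "A subject with multiple adverse events within a body system is only counted once towards the total of this body system and treatment". Protocol 11.4.1 and 11.4.4.4 plan the same table, and the Protocol's counting rule has nearly the same words: "A subject with multiple adverse events within a body system is only counted once towards the total of this body system". None of these places visibly limits the table to events after dosing or divides it by period.

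Protocol 9.1.1 defines an AE as an event arising "after providing written informed consent for participation in the study until the end of study visit". Protocol 8.4 ends medical history at the same point: "Relevant medical history/current medical conditions data will also be collected until signature of informed consent". SAP Section 4 defines the population: "The safety analysis set will include all patients who received any study drug".

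For vital signs, ECG and laboratory data, SAP 7.2 says: "Summary statistics will be provided by treatment (LNA043 20 mg vs. placebo) and visit/time". The AE table has no such time element.

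**The concern.** Safety and tolerability of a single injection is a primary objective (Protocol 2.1), and this is the only visible AE summary table. Two features of the design make its timing matter.

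First, anything new during screening, which can last 42 days, is recorded as an AE rather than as history. The safety set selects patients, not events, so it does not remove a dosed patient's screening events. Taken literally, the table could count such an event under a treatment not yet given.

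Second, the AE period contains a second, open operation at about Week 4 (Protocol 3.1). Each patient counts once per body system. A patient with an event soon after the injection and a patient with an event only after the later surgery therefore look the same in the body-system total. In a preferred-term row this happens only if the same term occurs in both periods. If post-surgery risk is equal in the two arms, pooling shrinks an early between-arm difference. If LNA043 changes post-surgery events, pooling mixes two effects.

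**Working it through.** There is no planned figure to reproduce. The check covers the calendar, the possible size of the pooling, and what the other outputs already show.

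**Calendar (Protocol 3.1 and Table 8-1).**
- Screening, Day -42 to -1: up to 42 days.
- Injection to planned second surgery, Day 1 to 29: 28 days.
- Second surgery to end of study, Day 29 to 197: 168 days.
- Share of post-dose time after surgery: 168/196 = 85.7%.
- Range within the visit windows: surgery Day 34 and last visit Day 190 give 156/189 = 82.5%; surgery Day 24 and last visit Day 204 give 180/203 = 88.7%.
- Surgery four weeks late (Day 57), as an example of the permitted delay: 140/196 = 71.4%.

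These are planned times. SAP 1.4 records early termination, and the documents do not say whether it shortened follow-up.

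**Patients.** About 12 Cohort 1 completers at 2:1 give about 8 versus 4 (Protocol 3.1 and 6.2). The number dosed, which is what the safety set uses, is not given. At 8 versus 4, one patient moves a percentage by 1/8 = 12.5 or 1/4 = 25 points.

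**Size of the pooling, with assumed rates.** Let an arm's early risk in a row be p. Let q be the chance of a post-surgery event in that row for a patient with no early one.
- Pooled risk = p + (1 - p)q.
- With equal q, the difference between arms = (p1 - p0)(1 - q).
- Assume early events in 4 of 8 versus 1 of 4, which is 50% - 25% = 25 points.
- q = 25%: 25 × 0.75 = 18.75 points. q = 50%: 12.5 points. q = 75%: 6.25 points.

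Next, hold the early counts fixed and let X ~ Bin(4, q) and Y ~ Bin(3, q) be the added patients. The chance that the pooled table shows no difference or a reversal is P[(4 + X)/8 ≤ (1 + Y)/4].

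| q | 5% | 10% | 25% | 50% | 75% |
|---|---|---|---|---|---|
| Probability | 12% | 19% | 28% | 41% | 53% |

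The answer depends almost entirely on q, which the documents do not supply.

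Fixing the early counts also hides sampling noise. If 50% and 25% are instead the true early risks, exact binomials for 8 and 4 patients give these chances of no difference or a reversal:
- early-only table: 25%;
- pooled table at q = 25%, 50% and 75%: 34%, 42% and 54%.

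So a quarter of the problem is small numbers, which no split can remove.

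**What the other outputs show.** Protocol 9.1.1 records start and end dates and a Yes/No relationship to study treatment for each AE. SAP 7.2 displays all AE information by treatment group and subject. An event before the injection or after the second operation can be picked out there, patient by patient.

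**Screening events.** Such an event changes a row only if that patient has no other event in it. Nothing in the documents says how often that would happen.

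**The case for a change.** The strongest point on the other side is the onset rule. The visible AE part of SAP 7.2 carries no redaction mark, and two programmers following it could produce different tables. At 8 versus 4, a single screening event could move a row by 12.5 or 25 points. One sentence would settle it, and AE start dates are already collected. This stands as an observation about wording. It does not stand as a fault in the plan. Counting from first dose is the usual convention for a table by treatment received. SAP 1.1 also refers to RAP documents, in the plural, for detail on the report outputs. The SAP contents list shows only redacted material between 1.4 and 4, and the Protocol is redacted between 11.4.1 and 11.4.3. A rule could be in any of these, so its absence cannot be established.

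The case for a split at surgery is weaker. A whole-period count by arm is a fair between-arm comparison, since both arms are planned to have both operations, and no bias towards either arm is shown. The whole-period table should also stay the main summary in any case, because the Protocol raises possible antibody-mediated effects (3.7), which could appear late. A split would therefore only add a descriptive table. Its post-surgery part would be a post-randomisation subset with variable start dates. It would not separate the injection from the Day 1 arthroscopy either, because the two coincide; only the placebo comparison does that.

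The contrast with vital signs, ECG and laboratory data shows no inconsistency. Those are measured at scheduled visits, whereas AEs are recorded by onset date.

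**Conclusion.** No change to the plan follows. The missing onset condition is a gap that analysts fill sensibly, and it may already be filled in text that cannot be seen here. The split at the second surgery is an optional extra. The current SAP version is dated after database lock, so a table added now would be post hoc, and it would add little to a by-subject display that can be read in full at this size.

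The calendar shares are firm as planned time: 86% of post-dose days follow the second surgery, or 83% to 89% within the visit windows. The dilution and reversal figures rest on assumed event rates and on 8 versus 4 planned completers, so they show a mechanism and are not an estimate. The conclusion assumes that the by-subject display carries onset dates and relatedness, as the wording of SAP 7.2 and the fields in Protocol 9.1.1 imply. On that basis, the safety conclusion of this non-confirmatory study would not be expected to differ.
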